4.7 DISTINCT CLINICAL SCENARIO: OVERT HE DIAGNOSIS & INITIATION OF LACTULSOE THERAPY

If a subject in either group (treatment or control) is diagnosed with Overt HE, or prescribed lactulose for any clinical reason outside of study participation during the study period, their participation in the study will be terminated. An early termination visit will be conducted with the subject to collect outcome data including the SF-8, ANT and Follow-Up Health Questionnaire.

4.8 EARLY TERMINATION VISIT

If a subject discontinues participation in the study, the subject will be asked to complete all 28 Day Follow Up Assessments at the time of discontinuation including the SF-8, ANT and Follow-Up Health Questionnaire. If they choose not to complete them, their participation will be terminated immediately. All data collection prior to termination will be retained by the study team.

4.9 SUBJECT INCENTIVES

Participants will be offered a \$50 compensation for completing all activities in the trial.

5. MANAGEMENT OF ADVERSE EVENTS AND PROTOCOL DEVIATIONS

5.1 PROTOCOL DEVIATIONS

Minor protocol deviations that do not impact the safety of participants or the integrity of data must be recorded and reported to the Institutional Review Board (IRB) on an annual basis as part of standard continuing review. Major protocol deviations that may impact participant safety or the integrity of data are required to be reported to the IRB as an ORIO within 7 days of knowledge of the event.

5.1.2 Protocol Deviations may include the following items, among others:

- Enrollment despite meeting exclusion criteria
- Enrollment despite not meeting inclusion criteria
- Consent not obtained in accordance with IRB guidelines
- Baseline assessments not collected
- Outcome assessments collected outside of prescribed study window
- Outcome assessments not collected

5.2 ADVERSE AND SERIOUS ADVERSE EVENT DEFINITIONS & REPORTING

5.2.1 Adverse and Serious Adverse Event Definitions (AE & SAE)

In the Mi-Kristal study an AE is defined as any untoward or unfavorable physical, social or psychological occurrence in a participant that can be temporally associated with the subject's participation in the study, whether or not considered directly related to the subject's participation in the research. An AE is considered an SAE if the event results in death or permanent disability and is definitely related to the subject's participation in the study. However, due to the nature of the participants enrolled and low risk nature of the treatments, the AEs and SAEs recorded and reported to the IRB will be limited using the following guidance.

All hospitalizations will be reported as AEs. Other events that are not attributable to their participation in the study will not be reported as AEs, even if the data are collected for study purposes (e.g. car accident, stroke, myocardial infarction etc.). The exception to this standard is death, which will always be reported as either an AE or SAE. Additionally, expected clinical issues that subjects experience related to their ongoing medical care or chronic health problems will not be considered AEs unless it involves any of the above mentioned AE examples. Any AEs that are attributable to the study will be reported and adhere to the AE Reporting Timeline (see Table 3 below). The 28 ± 7 days end point is our final contact with subjects in which we will collect AE and SAE information. Events which qualify as AEs will be classified using the following IRB standards:

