5.2.2 AE Relatedness and Severity

For all AEs, the PI ([name]) will use his best judgment and indicate how related the AE is to the research procedures and intervention. He will assign the AE to one of the four categories below:

- **Definitely related:** The AE *is clearly related* to the intervention
- **Probably related:** The AE *is likely related* to the intervention
- **Possibly related:** The AE *may be related* to the intervention
- **Unlikely to be related:** The AE *is doubtfully related* to the intervention
- **Definitely not related:** The AE *is definitely not related* to the intervention

The PI will provide an AE severity:

- **Mild:** asymptomatic or mild symptoms; clinical or diagnostic observations only; no intervention indicated
- **Moderate:** minimal, local, or noninvasive intervention indicated
- **Severe:** Severe or medically significant, but not immediately life-threatening; hospitalization or prolongation of hospitalization indicated; disabling
- **Life-threatening:** Life-threatening consequences; urgent intervention indicated
- **Fatal**

The PI will AE level of expectedness:

- **Unexpected adverse events:** (i.e., has NOT been addressed or described in one or more of the following: informed consent document for this study, IRB application for this study, grant application or study agreement, protocol or procedures for this study, investigators' brochure or equivalent (for FDA regulated drugs or devices), DSMB/DSC Reports, published literature, other documentation)

- **Expected adverse events:** (i.e., has been addressed or described in one or more of the following: informed consent document for this study, IRB application for this study, grant application or study agreement, protocol or procedures for this study, investigators' brochure or equivalent (for FDA regulated drugs or devices), DSMB/DSC Reports, published literature, other documentation, or characteristics of the study population.

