5.3 CRITERIA OF INTERVENTION DISCONTINUATION

If the subject experiences any SAE that might be considered related to Mi-Kristal participation, the study coordinator will inform the subject to stop all intervention activities. The PI will decide whether to continue study activities thereafter. Every effort will be made to maintain the subject's participation in follow-up activities. If lactulose therapy is terminated before 28 days, the Day 28 outcome assessments will be collected within 5 days of lactulose termination.

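### The mandatory stop in 5.3 hangs on the narrow SAE definition in 5.2.1, so a reversible severe or life-threatening lactulose reaction does not trigger it

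*Combined protocol and SAP*

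**What the plan says.** Section 5.2.1 defines a serious event by two conditions joined together: "An AE is considered an SAE if the event results in death or permanent disability and is definitely related" to participation in the study. It then limits what is recorded and reported to the IRB, giving as its reason "due to the nature of the participants enrolled and low risk nature of the treatments". Admissions are placed below the SAE level: "All hospitalizations will be reported as AEs".

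Section 5.2.2 has the PI assign relatedness, severity and expectedness to each AE. The severe grade reads "Severe or medically significant, but not immediately life-threatening; hospitalization or prolongation of hospitalization indicated; disabling", and separate grades for life-threatening and fatal events follow it.

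Section 5.3 is the stopping rule. Its trigger is "If the subject experiences any SAE that might be considered related to Mi-Kristal participation". Its action is that "the study coordinator will inform the subject to stop all intervention activities". Next, "The PI will decide whether to continue study activities thereafter". If lactulose ends before 28 days, "the Day 28 outcome assessments will be collected within 5 days of lactulose termination".

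**The concern.** The order of steps in 5.3 (the coordinator acts, then the PI decides) is that of a provisional safety hold. Such a hold is most useful for a serious reaction that is still reversible, because withdrawing the drug can then change the outcome. The trigger uses the term SAE, and 5.2.1 confines that term to death and permanent disability. A hold has no purpose after death, so within the 5.2.1 definition the 5.3 stop can act only on permanent disability, and permanence is often unknown when the event begins.

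The harms at issue are ones the protocol names. Section 8.3 lists dehydration and disturbances of sodium and potassium as rare effects of lactulose. These can be serious and still resolve. At stake is whether a subject with such a reaction is told to stop at once, or keeps taking the drug until someone decides otherwise.

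**Working it through.** No arithmetic applies. The check is to apply the 5.2.1 definition to the 5.3 trigger, and then to look for any other rule that requires the drug to stop.

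**Step 1: the outcome condition.** Take a treated subject with severe dehydration and electrolyte disturbance that resolves with treatment, and suppose the PI judges it definitely related. It did not result in death or permanent disability, so under 5.2.1 it is an AE and not an SAE. The 5.3 trigger is not met.

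**Step 2: the relatedness condition.** Section 5.2.1 demands a definite link. Section 5.3 accepts a possible one ("If the subject experiences any SAE that might be considered related to Mi-Kristal participation"). If 5.2.1 is applied in full, every SAE is already definitely related and the qualifier in 5.3 does no work. If 5.3 is read as relaxing the link, more deaths and permanent disabilities qualify, but the outcome condition is unchanged. The Step 1 event fails on both readings.

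**Step 3: the severity grades.** Section 5.2.2 would grade the Step 1 event severe or life-threatening. No text ties either grade to SAE status or to stopping the drug.

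**Step 4: other provisions.**

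| Section | Trigger | Response | Mandatory hold? |
|---|---|---|---|
| 4.3.1, 4.3.2 | Frequent stools, or symptoms that worry the subject | Lower dose; staff alert by email and study phone line for frequent stools | No |
| 4.6 | Hospitalization caused by lactulose | Discussion with the PI, who may pause or end the drug | No, discretionary |
| 4.7 | Overt HE, or lactulose prescribed outside the study | Participation ends | Not a drug-reaction rule |
| 4.8 | Subject discontinues | Outcome assessments requested | Not a safety trigger |
| 5.2.2 | Any AE | PI grades it | No action attached |

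**Result.** No provision requires a hold for a serious, reversible, lactulose-related event. With admission, 4.6 guarantees a discussion. Without admission, the subject has dose-reduction advice, the call line where it applies, and PI grading, for which 5.2.2 sets no time limit and no consequence for dosing.

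**The case against.** The strongest reply is that 5.3 sets a minimum and does not forbid stopping in other cases. A reader might infer that lactulose can be stopped only for an SAE. The documents do not say so: 4.6 allows a pause or discontinuation without one, Section 2 allows for removals at the PI's discretion, and 8.3 lets subjects leave at any time. This stands. The gap concerns an automatic hold, not the power to stop.

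A reader might also infer that serious events without admission never reach the PI. That is not supported either. An event attributable to the study is reported under 5.2.1, and the PI, who also prescribes the drug, grades all AEs under 5.2.2. The alerts and call line in 4.3.1 and 4.3.2 give an escalation route for diarrhea, a plausible path to dehydration. These routes are real, but none holds the drug while the PI's view is awaited.

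A third inference is that 4.6 protects only subjects admitted to Michigan Medicine. Only its care-team contact carries that limit. The sentence on PI discussion of a lactulose-caused hospitalization has no site restriction.

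Finally, the sponsor can say that the narrow SAE definition is deliberate for a low-risk drug. That explains what is recorded and sent to the IRB. It does not address when the drug should be held. It is, however, a fair reason not to insist that every hospitalization become an SAE, and the remedy does not need that. It is also fair that Table 1 schedules no laboratory tests, so outside hospital an electrolyte disturbance would surface only through self-report or outside care. A hold rule can act only on what is reported.

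**Conclusion.** The point holds in limited form. The mandatory interim stop in 5.3 does not reach a reversible severe or life-threatening event, even one definitely caused by lactulose, and the relatedness wording of 5.2.1 and 5.3 conflicts. Discretionary routes to stopping exist, so what is lacking is a default hold pending PI review. The lack is clearest for serious reversible events without admission.

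The size cannot be given as a number. The documents state no rate for such events, 8.3 calls the relevant effects rare, and nothing shows how often the drug would continue for want of a hold. The conclusion rests on the text alone: that SAE in 5.3 carries its 5.2.1 meaning, and that no other section imposes a hold. It should be fixed because the change is small and protects subjects. It does not bear on the validity of the primary comparison.

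**What to change.** Change the trigger in 5.3 and leave the SAE definition as it is for IRB reporting. Suggested sense:

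- Lactulose is held for any SAE, or any AE that appears severe or life-threatening on the 5.2.2 scale, that might be related to lactulose (at least possibly related).
- The coordinator applies the hold provisionally. The PI then grades the event and decides whether to resume, reduce or end treatment. Grading stays with the PI, as 5.2.2 provides.
- A temporary hold does not count as termination for the 5.3 rule that brings the Day 28 assessments forward.
- State that the possible-relatedness threshold governs the hold, and that the definite-relatedness condition in 5.2.1 serves the reporting definition only.

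The cost is a wording amendment and probably a few more temporary holds. No event becomes an SAE because of it. The one analytic cost is that a hold that becomes permanent brings the outcome assessment forward, in the lactulose arm only, under the existing rule. Excluding temporary holds from that rule keeps this effect small.

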3. SF-8
4. ANT
5. AUDIT-C

4.3 INTERVENTION PROCEDURES

4.3.1 Lactulose Administration and Duration

Subjects randomized to the control are not required to complete any intervention activities or treatments. For subjects randomized to lactulose therapy, the following steps to implement the intervention will occur on Study Day 1:

1. The Principal Investigator (PI) will prescribe lactulose to subjects enrolled at Michigan Medicine. Lactulose (Kristalose) will be allocated to the patient in person at the University of Michigan through the Investigational Pharmacy. If enrollment procedures were conducted remotely, the patient will be allowed up to two weeks to schedule an appointment with the study coordinator to receive Kristalose.
2. Subjects will be instructed to take 20g of Kristalose (1 packet) in 4oz water twice daily for 28 days. All patients randomized to lactulose will receive standard counselling.
3. First, all subjects will be instructed to take the first dose on awakening and the second dose approximately 4 hours after the first dose.
4. Second, subjects will be asked to monitor their bowel movements (see section 4.3.2 Adherence Assessment below). If they achieve ≥ 4 bowel movements in one day outside of the adherence assessments, they will be asked to contact the study team directly and will be instructed to reduce their lactulose frequency to one 20g dose daily. No dose adjustments will be made to *increase* bowel movements. Study staff will be alerted via email if a subject reports more than 4 bowel movements per day. Subjects will be instructed to call the study phone line if their bowel movements do not decrease with a reduced dose. They will also be instructed to notify the study team if they are undergoing proctoscopy or colonoscopy and to avoid taking nonabsorbable antacids (like aluminum or magnesium hydroxide) with Kristalose since these may interfere with the lactulose activity.
5. Third, patients will be counselled on the side effects of lactulose including mild bloating, cramping or diarrhea. If the symptoms worry the patient, they will be instructed to reduce lactulose to one 10g dose on awakening and then to increase to 10g twice daily as tolerated.

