4.3.2 Adherence Assessment

During the 28-day intervention phase, all subjects will be contacted on Study Days 3, 6, 9, 14, 15, 21 and 28 via automated REDCap email or SMS text messages via Twilio service. Study Day 28 will only be collected via REDCap email or phone. These points of contact are to collect data about stool frequency and consistency among all subjects and therefore lactulose adherence in the treatment group. If the subject opts out of Twilio service, the subject can also receive these questions via REDCap automated email or a study coordinator will collect this data from the subject directly via phone or email. On Study Days 3, 6, 9, 14, 21 and 28 subjects will be asked the following questions:

1. "How many bowel movements did you have yesterday? Please respond with a whole number." *If 0-4 bowel movements are reported the subject will exit the survey. If >4, the subject will receive the following instructions:*

Since you had > 4 bowel movements yesterday, please reduce to **one** 20g dose of kristalose (1 packet) packet per day. Please call the study line at [contact] if you continue to have more than 4 bowel movements daily or with any questions or concerns.

On Study Day 15 subjects will be asked:

2. "Please reference the Bristol Stool Chart we provided to you to answer this question. How would you describe your stool looks today? Please respond with the applicable number, between 1-7. *All subjects exit survey after response.*

1. Separate hard lumps
2. Sausage-shaped but lumpy
3. Like a sausage but with cracks on its surface
4. Like a sausage or snake, smooth and soft
5. Soft blobs with clear cut edges
6. Fluffy pieces with ragged edges, a mushy stool
7. Watery, no solid pieces, entirely liquid

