4.4 FOLLOW-UP AND OUTCOMES

The final follow-up study visit will occur 28 days post-baseline (SD 28±5). Primary and secondary outcome data will be collected at this visit. The SF-8, ANT and Health Follow-Up Questionnaire (see Appendix H) will be conducted with all subjects. The Health Follow-Up Questionnaire contains several questions from the baseline Health History Questionnaire including hospitalization data, overall sleep quality (PSQI), number of falls, number of bowel movements per day and regular daily activity impairment score (WPAI). This visit will be conducted via REDCap email and/or phone.

Table 1. Procedure Table

	Entry/ Day 1*	STUDY DAY						
		3	6	9	14	15	21	28 (SD 28 ± 5 days)
Informed Consent	X							
Randomization	X							
Contact Information	X							
Demographics Questionnaire	X							
Health History Questionnaire	X							
Short Form Health Survey 8	X							X
Animal Naming Test	X							X
AUDIT-C	X							
Health Follow-Up Questionnaire								X
Twilio/REDCap Email Automated Messages		X	X	X	X	X	X	X
Lactulose Therapy	X	X	→					X

* Control Group: Study Day 1 is defined as the calendar day on which the subject is randomized.

Treatment Group: Study Day 1 is defined as the calendar day on which the subject receives Kristalose.

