8.3 POTENTIAL RISKS AND BENEFITS

There is minimal medical risk to any participant in this study. Patients will be counselled on the risk of cirrhosis complications (ascites, HE) that may be related to their underlying disease as well as side effects associated with lactulose: abdominal discomfort, bloating, diarrhea, dehydration and rarely hypernatremia and/or hypokalemia. Participants can withdrawal at any time. The potential benefits to participants include an improvement in HRQOL, cognitive function and overall sleep quality and reduction in the risk of developing HE.

The known or expected risks are:

- **Questionnaires:** Many of the questions relate to how the subjects are feeling, and this may lead to an emotional reaction. To minimize these risks, questions will not ask explicitly sensitive information and study coordinators will be available for support. Additionally, should the questionnaires or surveys become uncomfortable, subjects can choose to skip any question that they do not wish to answer or stop at any time.
- **Loss of confidentiality:** There is rare risk of loss of confidentiality or privacy. To reduce the risk of loss of confidentiality, trained members of the research team will ask subjects questions in a private patient room. This information will be limited to the subject's name, date of birth, sex, and subject ID. Information such as the subject's full name and phone number will be recorded along with their baseline data however, this information will be stored in a locked cabinet. This data will be entered into a password-protected database where all data will be coded using a study number and only staff involved in this research will have access to the data.
- **Lactulose:** There is the possibility that that lactulose can cause physical symptoms such as abdominal pain, diarrhea, and bloating. Lactulose can rarely cause dehydration and hypernatremia (low blood sodium) and/or hypokalemia (low blood potassium).

There may be additional risks that are unknown or unexpected.

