Appendix G. Health Follow-Up Questionnaire**Mi-Kristal Trial Follow-Up Health Questionnaire**

Instructions: Please answer the following questions to the best of your knowledge. Please record the date the form was completed on the top of this page.

1. Have you been hospitalized since you enrolled in this study?

No
 Yes

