6.1 If yes, number of hospitalizations: _____

2. During the past month, how would you rate your sleep quality overall?

Very Good
 Fairly Good
 Fairly Bad
 Very Bad

3. Have you had any falls since you enrolled in this study?

Yes
 No

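### Lactulose adherence is inferred from stool pattern, which cannot separate a reduced or missed dose from low response; no form shown asks the dose taken or most of the named side effects

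*Combined protocol and SAP*

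**What the plan says.** - **Adherence (section 4.3.2).** Subjects are contacted on Days 3, 6, 9, 14, 15, 21 and 28 to "collect data about stool frequency and consistency among all subjects and therefore lactulose adherence in the treatment group". Six of these contacts ask for the previous day's bowel movement count. Day 15 asks only for a Bristol stool type.
- **Dose changes (section 4.3.1).** Treatment starts at 20 g twice daily. Under item 4, a high stool count leads to one 20 g dose daily, and the subject is asked to contact the study team. Item 5 covers other side effects: "If the symptoms worry the patient, they will be instructed to reduce lactulose" to one 10 g dose, then up to 10 g twice daily if tolerated. It states no step for reporting the change.
- **Supply (section 4.3.3).** Each lactulose subject receives 2 packages of 30 packets, 20 g each. Doses dispensed are logged, and the pharmacy is responsible for reconciliation. No return or count of unused packets is described.
- **Named risks (section 8.3).** The list is "abdominal discomfort, bloating, diarrhea, dehydration and rarely hypernatremia and/or hypokalemia". The lactulose bullet later reads "Lactulose can rarely cause dehydration and hypernatremia (low blood sodium" before the bracket closes.
- **Last contact.** Section 5.2.1 calls the Day 28 end point "our final contact with subjects in which we will collect AE and SAE information". Section 4.4 adds: "This visit will be conducted via REDCap email and/or phone". The health form is Appendix G (section 4.4 calls it Appendix H). Two of its five items are "Have you been hospitalized since you enrolled in this study" and "Have you had any falls since you enrolled in this study"; the others are sleep quality, average daily bowel movements and activity impairment. Sections 4.7 and 4.8 reuse the form at early termination.

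**The concern.** The plan has a stated adherence measure, but that measure is not specific to adherence. Stool count responds to the drug, prompts a dose reduction, and is compared between arms under Aim 5 and the secondary endpoints.

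The one dose change a subject can make alone, for bloating or cramping, has no reporting step, whereas item 4 of the same section does have one. Section 5.3 also requires the Day 28 outcomes within 5 days if lactulose stops early. A subject who stops without saying so would not set that rule in motion.

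At stake is interpretation rather than validity. A comparison of SF-8 by randomised arm needs no dose data. But if it shows no difference, the trial could not say whether lactulose failed to help or whether many subjects had cut the dose because they could not tolerate it. The side-effect results would likewise reflect mainly what subjects chose to volunteer.

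**Working it through.** The plan gives no figure on this point, so there is none to reproduce. The check compares sections and adds simple arithmetic from sections 4.3.1, 4.3.3 and 4.4.

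**1. What a stool count can mean.** A low count in a lactulose subject fits at least four states: full dose with low response; doses missed; dose cut for symptoms under item 5; or dose cut after an earlier high count under item 4. In the last case a good responder who follows instructions ends up looking like a non-adherent subject. The count is asked on 6 of 28 days (6/28 = 21%) and stool form on 1 of 28 (3.6%).

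**2. Range of dose the instructions allow, and packets left at Day 28.** Assumption, for illustration: one regimen is held for all 28 days. Packets dispensed: 2 × 30 = 60.

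| Regimen | Total dose | Share of starting regimen | Packets left |
|---|---|---|---|
| 20 g twice daily | 28 × 2 × 20 = 1,120 g | 100% | 60 − 56 = 4 |
| 20 g once daily | 28 × 20 = 560 g | 50% | 60 − 28 = 32 |
| 10 g twice daily | 28 × 2 × 10 = 560 g | 50% | 4 if a new packet is opened each time; 32 if packets are split |
| 10 g once daily | 28 × 10 = 280 g | 25% | 60 − 28 = 32 if a new packet each time; 60 − 14 = 46 if split |

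The dispensing log shows 60 in every row, so it cannot tell the rows apart. A packet count would help but is not enough alone: 4 left fits 100% or 50%, and 32 left fits 50% or 25%.

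**3. Visit date.** Section 4.4 allows ±5 days. Full dosing to Day 23 leaves 60 − 23 × 2 = 14. At Day 28, 14 left also fits 18 days at two packets and 10 days at one: 60 − (36 + 10) = 14. A count has to be read with the visit date and the reported dose.

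**4. Side effects named in section 8.3 against scheduled questions.**

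| Named effect | Scheduled question |
|---|---|
| Diarrhea | Stool counts; Bristol type on Day 15 |
| Abdominal discomfort | None specific; the SF-8 has a general bodily pain item |
| Bloating | None |
| Dehydration | None |
| Hypernatremia | None |
| Hypokalemia | None |

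One of six is touched directly. Events that lead to admission could surface through the hospitalization item.

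**The case against.** The case on the other side has real force, and it limits the point.

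- **A reader might infer that tolerability and exposure go uncaptured.** The documents do not support that. Stool counts, the Day 15 stool type, staff alerts for high counts, the study phone line, the hospitalization item and early-termination visits all yield some tolerability data. More than 5 bowel movements a day is a prespecified adverse-event aim. Reductions prompted by a survey answer can be dated from that answer, at least as instructions given. Section 7.1 mentions case report forms for the intervention phase that are not reproduced, so the claim can concern only the forms and contacts shown.
- **A reader might infer that an emailed form can be the whole Day 28 contact.** Section 4.4 also requires the Animal Naming Test, and Appendix D has staff time and tally it. A completed visit therefore involves live contact at which symptoms could be mentioned. The plan still gives no question to prompt them.
- **A reader might infer that item 5 tells subjects not to report a dose cut.** It is silent on reporting; it does not waive it.
- **A reader might infer that the sodium wording would change how events are coded as expected.** Section 5.2.2 lists many sources for expectedness, including published literature and the study population, so that effect is speculative.
- **Limited recording is deliberate.** Section 5.2.1 restricts adverse-event recording because the treatment is considered low risk. That is a defensible choice for reporting to the IRB. It does not supply a measure of dose taken. A checklist in an open-label trial may also be answered differently by arm, which is a genuine cost.

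**Conclusion.** The point holds in limited form. The stated adherence measure cannot do its job, because stool pattern is at once proxy, drug effect, reduction trigger and outcome. Within the plan's own instructions, cumulative dose can range from 25% to 100% of the starting regimen, and no questionnaire or contact shown records which applied. The number of lactulose subjects affected lies between none and all of roughly 25; the documents give no basis for an estimate. Five of the six named side effects have no specific question and depend on spontaneous report.

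This rests on two assumptions: that the case report forms not shown do not already ask for dose and symptoms, and that reconciliation does not already include a packet count. If either is wrong, the remedy shrinks to stating it in the protocol.

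Secondary and editorial: in section 8.3 the term hypernatremia and its gloss as low sodium have opposite meanings.

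**What to change.** Add to Appendix G, for use at Day 28 and at early termination:

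1. **Both arms:** a short yes/no checklist of the symptoms named in section 8.3 (abdominal discomfort, bloating, diarrhea, dehydration), plus whether a doctor reported an abnormal blood sodium or potassium.
2. **Lactulose arm:** current daily dose; whether, when and why the dose was reduced or stopped; and packets remaining. Read the packet count against the actual visit date and the reported dose.

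Report dose taken from these items instead of inferring adherence from stool pattern, and keep stool count as an outcome. State in section 4.3.3 how reconciliation is done when the final visit is remote. Reconcile the Day 28 window, which is ±7 days in section 5.2.1 and ±5 in section 4.4. In section 8.3, make the sodium term and its gloss agree, and check the consent wording.

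The cost is a handful of items on an existing form, some wording and a minor amendment. No dosing rule, eligibility criterion or endpoint changes. The downsides are more mild symptoms to review and possible differential reporting between open arms, so checklist results should be presented with that caveat.
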